### 2.2. FACTORS ASSOCIATED WITH POOR TB TREATMENT OUTCOMES

Relative impact of potentially modifiable host factors (e.g. HIV, DM, smoking, IAP, alcohol misuse, under-nutrition, mental health status) on treatment outcomes such as failure, recurrence or death is not well established in populations including Indians. While most patients treated for TB are cured of TB, poor outcomes such as treatment failure, recurrent disease and death remain important challenges. Approximately 85% of Indian patients who are treated for active smear-positive PTB via the Directly Observed Therapy Strategy (DOTS) are cured (AFB smear and culture negative). However, 2% fail (remain smear positive at 5 months of treatment), 6% die on treatment, and the remainder default or transfer out. Furthermore, approximately 12% of cured patients develop recurrent TB within 18 months of treatment, either due to relapse of the same strain or re-infection from others in the community. A patient's second course of TB treatment is more than twice as likely to fail, and more than 4 times as likely to involve MDR-TB. As shown in *Table 1*, poor treatment outcomes are linked to potentially modifiable host factors though with variable quality of evidence and estimations of individual contributions.

**HIV** has clearly been shown to increase TB treatment failure, death and recurrence and low CD4 counts increase that risk further [2,3]. While HIV is an important risk factor at the individual level, it is not likely to be a primary driver of poor treatment outcomes in India's TB epidemic as only 0.3% of India's population has HIV and only 2-15% of Indian patients with TB have HIV co-infection.

Though **Diabetes Mellitus (DM)** increases risk of TB two-fold compared to 22 times for HIV, DM is estimated to account for at least 20% of smear positive PTB cases in India [4-6], making it a more relevant risk factor in this setting. Most but not all data suggest that DM is associated with reduced 2-3 month sputum conversion, increased mortality (pooled RR of 1.89 based on 23 studies) [7] and may be a risk factor for TB recurrence and relapse (RR of 3.89) [7] but few studies have adjusted appropriately for confounders. It is unknown if DM is associated with acquired drug resistance.

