**TABLE 1: SCHEDULE OF EVALUATIONS FOR ACTIVE TB COHORT**

CRF   Time	Entry	2W	4W	8W	5M	6M	12M	18M	24M	End of Tx	TB recurrence (failure, relapse)
Consent/Enrollment	X										
Medical History	X										
Psychosocial Interview	X			X		X	X	X		X	X
Socio-demographic Interview	X										
Clinical Assessment (i.e. TB and Lung Health Assessment, Physical examination  , Concomitant Meds, Diagnoses/AEs)/ Medication History	X	X	X	X	X	X	X	X	X	X	X
TB Medication Adherence	X	X	X	X	X	X				X	
Nutrition Assessment 	X					X				X	X
Anthropometrics 	X	X	X	X	X	X	X	X	X	X	X
Chest Radiograph 	X			X		X					X
Sputum AFB and culture X 2 (DST if culture+) 	X	X	X	X	X	X		X		X	X
Sputum for Cepheid Gene-Xpert X 2	X										X
Extrapulmonary TB sample for AFB and culture/histopathology	X 										X
Hematology (CBC)	X			X							X
HIV Test (if not already known)	X										X
CD4 count if HIV +ve 	X										X
Hemoglobin A1c (Adults) 	X									X	X
LFT	X		X	X						X	X
Chemistry (Renal panel, glucose)	X									X	X
Urinalysis	X										X
Urine Pregnancy test	X			X		X					X
PFT (Adults), Spirometry (Child) (random subset)				X						X	X
Samples for Biorepository	Entry	2W	4W	8W	5M	6M	12M	18M	24M	End of Tx	TB Recurrence
Stored Plasma sample for PK 			X		X						
Stored Plasma	X		X	X		X	X		X	X	X
Whole Blood for DNA				(X) 							
Stored Sputum	X	X	X	X		X				X	X
Stored Urine	X		X	X		X	X		X	X	X

Stored Hair	X		X		X	X				X	X
Stored Mtb isolate	X			X	X	X					X
Whole Blood for Host mRNA (PAXgene)	X		X	X		X	X		X	X	X
Whole Blood forPBMC	X		X	X		X	X		X	X	X
Whole blood for Quantiferon supernatant	X		X	X		X	X		X	X	X

 Active TB participants with Microbiological Confirmation of TB (defined as smear+, Xpert+, or smear negative but cultured confirmed. Patients who are initially negative by smear and/or Xpert will be enrolled if they meet criteria for Cat-1 TB treatment. Participants who remain culture negative by 3 months will be follow-up but will not be included in the primary analysis.

 An additional 'End of Rx' time-point to be observed for participants with Rx duration exceeding 6 months

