## 8. ASSESSMENT OF OUTCOME

*Aim 1: To examine the host and microbial factors associated with TB treatment outcomes*

- Primary outcome for Aim 1 will be a composite poor treatment outcome, defined as treatment failure, recurrence or death within 24 months of TB treatment initiation.
- Secondary outcomes will include time-to-sputum AFB negativity, time-to-culture negativity, and time-to-detection of MTB using liquid sputum culture on mycobacteria growth indicator tubes (MGIT).

*Aim 2: To investigate the host and microbial factors associated with the progression from infection to active TB disease*

- Primary outcome is incident TB within 24 months (best outcome to assess what factors are associated with the risk of progressing to active TB)
- Secondary outcome will be proportion with co-prevalent TB at time of initial household screening.

*Aim 3: To explore the host and microbial factors associated with MTB transmission*

- Primary outcome will be incident infection defined as conversion of TST or QGIT or at entry a positive TST (> 15mm) or QGIT in a child <5 years.
- Secondary outcome will be prevalent active TB at entry or incident TB among HH contacts that have the same DNA fingerprint using MIRU based genotyping at NIRT.

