#### **Bacteriologic outcomes, drug-susceptible (DS) TB:**

1. **DS bacteriologic cure:** By the end of the RNTCP-specified standard, first-line multi-drug TB therapy, the participant has two or more consecutive respiratory secretion cultures negative for *M. tuberculosis*, and no evidence of bacteriologic failure.
2. **DS bacteriologic status indeterminate:** By the end of RNTCP-specified standard, first-line multi-drug TB therapy, the participant has resolution of symptoms of tuberculosis, but has not had two or more consecutive respiratory secretion cultures performed to establish cure status.

3. **Bacteriologic failure:** By the end of RNTCP-specified standard, first-line multi-drug TB therapy, the participant has one or more specimens from the respiratory tract or extra-pulmonary site that are culture-positive for *M. tuberculosis* in either liquid or solid media (with any colony count), when the culture has not been determined to be a false-positive culture.

**DS bacteriologic recurrence** Among participants who did not experience a clinical (as described below) or bacteriologic failure of therapy, the participant has a clinical specimen collected from any site during the follow-up phase that is culture-positive for *M. tuberculosis* in either liquid or solid media (with any colony count), when the culture has not been determined to be a false-positive culture.

**Clinical outcomes:** Participants who do not meet bacteriologic criteria to establish their final status may be assigned a clinical outcome.

1. **Clinical response:** A participant who has resolution, by the end of therapy, of symptoms attributable to tuberculosis.
2. **Clinical failure:** The persistence, progression, or recurrence of signs and symptoms of tuberculosis (fever, sweats, productive cough, documented weight loss, worsening of chest radiograph, progressive evidence of extra pulmonary tuberculosis) that is determined by the principal investigator (PI) to be due to tuberculosis and not due to another underlying cause.
3. **Clinical relapse:** Clinical or radiographic evidence of active tuberculosis after completion of therapy but before the end of the follow-up phase.

In addition to disease outcome status, participants will be categorized regarding completion of treatment status, defined as follows:

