## 9. STATISTICAL CONSIDERATIONS

### 9.1. SAMPLE SIZE AND ANALYSIS PLAN

**Aim 1.** The Active TB Cohort will include 800 adult PTB cases, 200 adult EPTB cases and 200 pediatric TB cases. The primary analysis set will be 800 adult PTB patients. Secondary analysis sets will include EPTB and pediatric TB.

Primary outcome is poor treatment outcome defined as failure, recurrence or death. Secondary outcomes will include time to AFB smear negativity, time to sputum culture negativity; time to detection of MGIT positivity. Host factors age, sex, DM, HIV, IAP exposure, tobacco exposure, malnutrition, and mental health will be key predictors for poor treatment outcomes.

Person-years of follow-up will be calculated for each member of the analysis set. Of TB patients who experience the outcome of interest, person-years of follow-up will be calculated as number of years between date of enrollment and date of event. Among those without the outcome person-years will be the number of years between enrollment and last date of follow-up. Crude treatment failure rates and 95% exact Poisson confidence intervals in the presence and absence of primary risk factors will be calculated. Adjusted treatment failure rate ratios will be estimated using multivariate Poisson regression models with person-years of follow-up as an offset. The Poisson regression models will also investigate interaction between individual and HH factors that might influence treatment outcomes.

A secondary subgroup analysis (may not be sufficiently powered) by enrollment sites, NIRT and BJMC, will be performed by adjusting the level of significance using a Bonferroni adjustment.

**Aim1 Power.** For Aim 1, we expect 20% (n=160) of 800 adult PTB cases will have the composite primary outcome (2% will fail, 6% will die, and 12% will have recurrence). This study will have at least 90% power at 5% level of significance to identify host and microbial risk factors (enumerated in section 3B3), with a prevalence of 10% - 40%, associated with poor treatment outcomes with relative risk ratio ranging from 1.5 to 6.0 over 24 months of follow-up.

**Aim 2.** The analysis set is individuals in the HH Contact Cohort: 3200 HH contacts of 800 PTB patients.

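### Bacteriologic failure in the Aim 1 composite has a latest time but no earliest time, so early on-treatment positive cultures count as failures

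*Protocol*

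**What the plan says.** Section 8 sets the Aim 1 primary outcome as a "composite poor treatment outcome, defined as treatment failure, recurrence or death within 24 months of TB treatment initiation".

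Section 8.1, bacteriologic outcomes, item 3, gives the condition for the failure component: "By the end of RNTCP-specified standard, first-line multi-drug TB therapy, the participant has one or more specimens from the respiratory tract or extra-pulmonary site". The test is culture, and a single positive result suffices, however few the colonies, unless it is judged to be false. No earliest visit, prior conversion or exclusion of early cultures is given.

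Other categories depend on this one. Cure needs two or more consecutive "cultures negative for *M. tuberculosis*, and no evidence of bacteriologic failure". Bacteriologic recurrence opens with "Among participants who did not experience a clinical (as described below) or bacteriologic failure of therapy, the participant has a clinical specimen collected" during follow-up. Completion of adequate therapy also requires that the patient not be a treatment failure.

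In the schedule of evaluations for the Active TB Cohort, the row "Sputum AFB and culture X 2 (DST if culture" positive) is marked at entry, 2W, 4W, 8W, 5M, 6M and End of Tx. Section 6.3 lists the same on-treatment times. Footnote 1 of that schedule leaves participants who are still culture-negative at 3 months out of the primary analysis.

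Section 9.1 plans 160 composite events among 800 adults with pulmonary TB: 2% failure, 6% death and 12% recurrence. The one time-anchored description of failure is in the background, section 2.2: "2% fail (remain smear positive at 5 months of treatment").

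For the analysis, section 9.1 states: "Crude treatment failure rates and 95% exact Poisson confidence intervals in the presence and absence of primary risk factors will be calculated".

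**The concern.** The rule says when counting stops but not when it starts. A positive culture at diagnosis or in the first weeks of treatment is expected in this population. Section 8 itself makes time to culture negativity a secondary outcome, and the schedule stores isolates at 8W. A definition that counts those cultures would label ordinary early positivity as a primary-outcome event.

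At stake are the number of Aim 1 events, their timing and their meaning. Section 9.1 measures person-years from enrollment to the event, so an event dated to an early culture also shortens the person-time in the Poisson offset, to about zero if the entry culture counts. A risk factor for slow early conversion could then appear as a risk factor for poor treatment outcome.

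A smaller point sits beside this. Section 9.1 names the composite as primary, then describes rates and rate ratios of treatment failure, which is only one component.

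**Working it through.** **1. The plan's own figure.** Section 9.1: 800 × 0.02 = 16 failures; 800 × 0.06 = 48 deaths; 800 × 0.12 = 96 recurrences. The sum is 160, or 20%. It reproduces.

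**2. Item 3 as written.** Let c be the culture-confirmed share of the 800. Every such participant has a positive culture before the end of therapy, so failures = 800 × c.

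- Footnote 1 of the schedule implies c close to 100%: 800 failures, which is 800 / 16 = 50 times the plan. Cure and bacteriologic recurrence are then empty, and every factor has a risk ratio of 1.0 for the composite.
- With c assumed at 80% to 95%, there are 640 to 760 failures. If the rest carry the planned 20% risk, composite events are 800 × (c + 0.2 × (1 − c)) = 672 to 768, or 84% to 96%.
- At 84% overall risk and exposure prevalence f, the largest possible cumulative risk ratio is 1 / p0, with p0 = (0.84 − f) / (1 − f). For f = 10%, p0 = 0.74 / 0.90 = 0.822 and the ratio is 1.22. For f = 40%, p0 = 0.44 / 0.60 = 0.733 and the ratio is 1.36. Both lie below the 1.5 at which the planned range begins.

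**3. Entry culture set aside, early on-treatment cultures kept.** Let q be the share positive at 8W. The protocol gives no value, so 10% to 30% is an assumption.

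- Failures from 8W alone are 800 × q = 80 to 240. Positives at 2W and 4W could only add to this.
- If the planned late failures are among the 8W positives, and there is no overlap with death or recurrence, composite events are 800 × (q + 0.18) = 224 to 384.
- With the greatest possible overlap, composite events are the larger of 160 and 800 × q, so 160 to 240.

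At q = 10% the total therefore lies between 160 and 224, and at q = 30% between 240 and 384.

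**4. Late window only.** If failures in a late window occur at the planned 2%, the counts return to 16 and 160. That 2% matches a smear result at 5 months (section 2.2), whereas item 3 rests on culture. The documents do not show that a culture-based late window would also give 2%.

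**The case against.** The strongest reply is that nobody would apply item 3 literally, and the protocol supports that reply.

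- Table 4 stores the original isolate separately from a relapse or failure isolate.
- The schedule gives failure and relapse an event column of their own, apart from the entry and early visits.
- Cure, indeterminate status and failure all open with the same reference to the end of therapy, so they can be read as parallel end-of-treatment categories.
- The planned 2% and 12% cannot coexist with universal failure.

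This stands against one tempting inference, that the Aim 1 composite will collapse in practice. The documents show that a later culture was intended. They do not say which one: Table 4 excludes at most the entry culture, and nothing states whether a positive at 2W, 4W or 8W counts.

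A second reply is that an analysis plan not shown here may set the window. It may, but the protocol does not defer the definition. It states one, which the analysis plan would have to override.

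Three further inferences do not hold:

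- **Sites classifying differently.** Item 3 is a culture rule, the data sit in one shared web-based system, and investigator judgement enters only clinical failure.
- **The 5-month mark as the study's rule.** It is a smear-based background figure for the national programme.
- **Failure alone as the primary model.** Section 9.1 names and powers the composite, so its later wording is best read as loose terminology.

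**Conclusion.** The point holds in a limited form. Item 3 lacks a lower time bound, and no other section supplies one. Its literal result (800 of 800 failures, or 640 to 760 if 80% to 95% are culture-confirmed) contradicts the 16 planned. It shows that the sentence is wrong, but it does not forecast the analysis.

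The practical defect is that early on-treatment positives are not excluded. They would change a component of the primary outcome by an amount that the documents do not fix. The 80 to 240 failures rest entirely on the assumed 10% to 30% positivity at 8W. At the low end, with full overlap, the composite total would not move at all, although the dates and types of events would. Because cure, bacteriologic recurrence and completion of adequate therapy all depend on this definition, it should be corrected before outcomes are classified.

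**What to change.** Amend section 8.1, item 3, so that for the analysis endpoint only cultures from a stated late-treatment window count as failure. Exclude entry and early on-treatment cultures explicitly. The window should come from cultures already scheduled (5M, 6M, End of Tx). The choice is the sponsor's, and 5M onward is one option.

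Apply the same window to the two negative cultures required for cure. Footnote 13 of the schedule pools the two follow-up specimens for testing, so check that the chosen window can supply two consecutive cultures.

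Reconcile sections 2.2, 8.1 and 9.1: say that the 2% planning figure is smear-based at 5 months while the endpoint is culture-based, and either justify 2% for culture or show a range.

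In section 9.1, replace treatment failure with poor treatment outcome wherever rates and rate ratios are described, so that the model matches the composite.

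The cost is a few sentences in three sections. No visit or test is added, and because the change concerns classification for analysis, no participant's treatment is affected.

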**Completion of therapy status:**

1. **Completion of adequate therapy:** Considered accomplished when the patient is not a treatment failure and has received the number of doses of RNTCP-specified multi-drug anti-TB therapy recommended, depending on their initial disease status categorization (DS or DR).
2. **Incomplete:** Treatment is considered incomplete if the subject has defaulted from treatment, defined as treatment interruption for two or more consecutive months.

## **8.2. OUTCOME MEASURES FOR HH CONTACT COHORT (COHORT B)**

**Active TB** is the primary outcome measure of interest in this cohort and will be defined as the following:

- a. No TB: Participant had no indication of MTB (pulmonary or extra-pulmonary) over follow up period
- b. Definite case: Culture-confirmed TB from any anatomic site.
- c. Probable case: Adult ( $\geq$  age 14) with symptoms of TB plus acid-fast bacilli seen on microscopic examination of sputum or biopsy specimen, but without culture-confirmation.
- d. Probable case: Child (<14) defined as:
  - i. Symptoms consistent with TB, specifically fever or cough for 2 weeks, or loss of weight or failure to gain weight normally, plus a history of contact with a suspected or confirmed case of active TB AND
  - ii. Acid-fast bacilli seen on microscopic examination of sputum or biopsy specimen  
OR  
Culture-negative after 2 attempts at sputum collection, using sputum induction, nasopharyngeal aspirates or gastric aspirates and have chest radiography that is consistent with intra-thoracic disease due to Mycobacterium tuberculosis.
  - iii. AND there is at least 1 of the following:
    - 1. A positive clinical response to standard multidrug anti-tuberculosis treatment OR
    - 2. Documented exposure to a case of active TB.
  - iv. AND immunological evidence of M. tuberculosis infection (e.g, reactive TST or positive IGRA)
- e. Possible case: Adult or child diagnosed with extra-pulmonary TB based on radiographic or other evidence, but without culture-confirmation.

**Incident MTB infection** is the secondary outcome measure in this cohort and will be defined as a positive TST or QGIT in children < 5 years or seroconversion of TST or QGIT among HH contacts during follow up.

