Specific Aim 2 Disease Progression	1. Host markers of inflammation, oxidative stress, IAP, nicotine and risk of development of active TB (Year 3) 2. Impact of HIV, DM, tobacco, IAP and other modifiable risk factors on development of active TB (Year 5) 3. Estimate risk of disease progression by TST/QGIT status in adults and children (Year4,5)	1. Biosignatures of latency and active TB (Year3,4) 2. Host response to 16 novel Mtb antigens for diagnosis of LTBI and active TB (Year 3,4) 3. Differential expression of PGLYR and NOD proteins in different stages of infection (Year 3,4)	1. Compare index Mtb and HH incident TB strains to determine if specific Mtb strain types are associated with development of active TB (Years 4,5)	1. Microbial transcriptomebiosignatures associated with progression to active disease (Years 3,4)
Specific Aim 3 Transmission	1. Within HH transmission dynamics (Year 4,5) 2. Relative contribution of HIV, DM, smoking, IAP and other modifiable risk factors on TB transmission(Year 5)	1. Host sputum and peripheral blood inflammation markers, sputum macrophage function, in IAP and/or tobacco exposed and risk of increased host susceptibility (Years 3,4)	1. Compare Mtb strain sequences and drug susceptibility patterns of transmitters vsnontransmitters(Years 4,5)	1. Microbial transcriptomebiosignatures associated with transmission of Mtb infection (Years 3,4)

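### Child probable TB in section 8.2 requires a positive TST or IGRA, so within that tier the Aim 2 study of progression by TST/QGIT status has its exposure built into its outcome

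*Protocol*

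**What the plan says.** Section 8 sets the Aim 2 endpoint: "Primary outcome is incident TB within 24 months". Section 8.2 says that active TB "is the primary outcome measure of interest in this cohort and will be defined as the following", and then grades cases as definite, probable or possible.

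- Definite, any age: "Definite case: Culture-confirmed TB from any anatomic site".
- Probable, adult (14 or older): a person "with symptoms of TB plus acid-fast bacilli seen on microscopic examination of sputum or biopsy specimen, but without culture-confirmation".
- Probable, child (under 14): four items, i to iv. Item i is symptoms plus a contact history. Item ii is a positive smear or biopsy, or two negative culture attempts with a compatible chest radiograph. Item iii is a treatment response or "Documented exposure to a case of active TB". Item iv is "AND immunological evidence of M. tuberculosis infection (e.g, reactive TST or positive IGRA".
- Possible, any age: "Possible case: Adult or child diagnosed with extra-pulmonary TB based on radiographic or other evidence, but without culture-confirmation".

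Only the child probable tier asks for a TST or IGRA result.

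Table 1 (study objectives and timeframe) lists, as the third clinical/epidemiological study under Specific Aim 2, "Estimate risk of disease progression by TST/QGIT status in adults and children (Year4,5". Nothing in the protocol limits that study to definite cases or sets item iv aside for it.

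Table 2 (household contacts schedule) places TST and QGIT at entry, 4, 12 and 24 months, with follow-up tests only if the previous one was negative. At the active TB visit it schedules QGIT but not TST; section 6.3 also lists QGIT at TB activation.

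**The concern.** When the test result is both the exposure and a condition for being counted as a case, part of the association is produced by the definition. Take two children with the same symptoms and the same compatible radiograph, both culture-negative. The one who tested positive at entry is a probable case. The one who tested negative at entry, and is still negative at diagnosis, is not. The error runs one way: it lowers observed risk in test-negative children, raises the child risk ratio, and makes a negative test look more reassuring than it is. The purpose of the listed study is to say how far test status predicts progression, so this is the quantity that the definition distorts.

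**Working it through.** **The plan's own figure.** The only number attached to this outcome is the expected count of incident cases in section 9.1. Latently infected: 3200 × 0.40 = 1280. Recently infected: 1280 × 0.25 = 320. Cases among them: 320 × 0.15 = 48. Background: 3200 × 0.0037 × 2 = 23.68. Total: 48 + 23.68 = 71.68, which rounds to the stated 72. It reproduces, and this point does not dispute it. It is not split by age or case tier, so it does not supply the inputs needed below.

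**Size of the distortion.** Let R be the true two-year risk, equal in children who test positive and negative at entry. Define:

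- p = share of child cases that can qualify only as probable (neither culture-confirmed nor extra-pulmonary);
- c = share of those, among children negative at entry, who test positive by diagnosis.

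Children positive at entry all meet item iv, so their observed risk is R.

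Among children negative at entry, a share 1 − p of cases is counted through the definite or possible tiers. Of the remaining share p, a fraction c is counted. Observed risk = R(1 − p) + Rpc = R[1 − p(1 − c)].

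False risk ratio = 1 / [1 − p(1 − c)].

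The documents give neither p nor c, so these are assumed values:

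| p | c = 0.5 | c = 0 (extreme) |
|---|---|---|
| 0.25 | 1/0.875 = 1.14 | 1/0.75 = 1.33 |
| 0.50 | 1/0.75 = 1.33 | 1/0.50 = 2.0 |
| 0.75 | 1/0.625 = 1.60 | 1/0.25 = 4.0 |

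The factor is 1 only if p = 0 or c = 1. If the true ratio is not 1, it is multiplied by the same factor.

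**Which test status is the exposure.** The protocol does not say whether status is taken at entry or updated during follow-up. With entry status, conversion before diagnosis softens the effect, as c shows. With status updated to diagnosis, a test-negative child could hardly ever be a probable case, because TST and QGIT are the only infection tests scheduled in contacts.

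**How item iv attaches.** The alternative inside item ii could be read so that iv applies only to the culture-negative radiographic branch. The numbering i to iv favours applying it to every child probable case. On the narrower reading p is smaller, but the mechanism is the same.

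**The case against.** Much can be said on the other side, and a good part of it stands.

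- **The possible tier.** Counting every case without culture confirmation as dependent on item iv would be wrong, because extra-pulmonary cases need neither culture nor a test. Section 2.3 says that young children are more prone to disseminated disease, so this tier need not be small. With an assumed 25% definite and 25% possible, p is 0.50, not 0.75, and the false ratio is 1.33 rather than 1.60 at c = 0.5, or 2.0 rather than 4.0 at c = 0. The formula above allows for this.
- **Repeat testing.** A child negative at entry has several scheduled chances to convert, and either test suffices. The column c = 0 is an extreme, not an expectation.
- **Coherence of item iv.** Aim 2 concerns progression from infection to disease, so asking for evidence of infection when culture is negative is a reasonable specificity choice for the general endpoint. Test status is one listed study, not the Aim 2 primary outcome. That limits where a change is needed; it does not remove the overlap in the study where test status is the exposure.
- **Tier-specific analysis.** The grading already permits a definite-only analysis. The protocol does not call for one here, and as written all tiers fall under active TB.

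Four stronger inferences are tempting, and the documents do not support them. One is that item iv alone decides who counts: item iii is met by every household contact, but items i and ii still discriminate. A second is that children who do not react drop out of the Aim 2 primary outcome: those with culture-confirmed or extra-pulmonary TB stay in. A third is that item iv by itself makes adult and child results non-comparable: the adult definition requires acid-fast bacilli and the child definition has a radiographic route, so they would differ anyway. A fourth is that HIV or undernutrition would be made to look protective: nothing in the protocol establishes that step, and HIV testing in child contacts is limited by note 6 to Table 2.

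**Conclusion.** The point holds, confined to the child probable tier and to the analysis by TST/QGIT status. There the exposure is a condition of the outcome, and the bias is upward in the child risk ratio. With true risk equal, and p between 0.25 and 0.75, the definition alone yields a ratio of 1.14 to 1.60 if half of the test-negative probable-only cases convert by diagnosis, and 1.33 to 4.0 if none do. These are illustrations on assumed p and c. They also assume that every child positive at entry meets item iv and that test status is taken at entry. The direction does not depend on the values chosen; the size does. The general Aim 2 case definition and the adult results are not called into question.

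**What to change.** For the TST/QGIT-status analysis only, state in section 8.2 or the SAP that:

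1. the exposure is TST/QGIT status at entry;
2. child probable cases are classified on items i to iii, without item iv;
3. a sensitivity analysis is restricted to culture-confirmed (definite) cases;
4. the current definition is reported as a secondary analysis.

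Leave the general Aim 2 case definition unchanged.

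This costs wording only, since symptoms, smear, culture, radiograph and test results are already scheduled. The downside is some false-positive probable cases, and it may not be trivial, because item iii is met by every household contact. As an illustration, the section 9.1 background rate, which is not specific to children, gives 0.37% × 2 = 0.74% over two years. An assumed 1% false-positive rate would raise that to 1.74%, about 2.4 times (1.74/0.74). False positives arising equally in both groups would pull a true ratio above 1 towards the null. The definite-only analysis is the check on this, because it depends on neither item iii nor item iv.
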